We will define those patients diagnosed in the 'post COVID-19 period' as from the start of the first national lockdown in England (March 11th 2020), and those in the preceding period as 'pre-COVID-19'. We will calculate the proportions of patients who received either 'curative intervention' for periods before and after the onset of COVID-19. The interpretation of the results will consider the specific time-period and context; for example, recognising that the provision of cancer services may reflect different organisational factors and pressures, such as those arising from the COVID-19 pandemic.

WP 2.2 Analysis

We will describe baseline characteristics of the study populations during the 'pre COVID-19' and 'COVID-19' periods, overall, and stratified by sociodemographic characteristics. We will report the total numbers of patients per quarter with each early-stage tumour during the 'pre' and 'COVID-19' periods, and the proportions who had curative RT and surgical treatments. We will report these proportions overall, and according to sociodemographic characteristics (e.g. age, sex, deprivation, ethnicity). We will address missing data with multiple imputation approaches, apart from for missing ethnicity data, for which we will define an 'unknown' category recognising that these data may be 'missing not at random'.

We will develop mixed-effect multivariable, multinomial logistic regression models to assess first, the proportions receiving curative RT and surgical strategies versus no curative intervention according to sociodemographic characteristics prior to COVID-19. Second, we will assess whether these inequalities changed during COVID-19 compared to previous periods.

Each model will adjust for other patient characteristics (e.g., comorbidity, frailty levels, performance status and cancer stage, distance to centre), time period, seasonality and allow for clustering within NHS trust hospitals and cancer alliances (random effects). In sensitivity analyses we will assess the robustness of results to, alternative standpoints, for example alternative approaches to handling the missing data, and exclusion of the first wave of COVID-19 (1st February to 30 June 2020) given the atypical nature of the care provided during this period.

WP 2.3 Outputs

For each tumour type, we will report the association of sociodemographic characteristics on the use of either curative intervention versus non-curative interventions prior to the onset of the pandemic. We will report the impact of COVID versus pre-COVID periods on the corresponding probability of receiving either curative modality, overall and according to sociodemographic characteristics.

We will draw from the findings of WP1 to contextualise these findings, recognising that curative treatment is within a complex care pathway, and may also reflect local organisational and patient factors beyond those measured in the routine data.

WP 3: To assess the effectiveness of curative RT versus surgery (Objective 3) (lead [name], unless stated)

The third WP will assess the effectiveness of curative RT versus surgery using a target trial design to ensure comparability of the treatment groups (21). We will conduct a separate target trial of curative RT versus surgical strategies for each tumour type. The provisional definitions of target populations, and comparison groups are listed in Table 2. These definitions will be finalised by the clinical panels in WP1. We will address the risk of residual confounding, with an instrumental variable analysis, as this can provide consistent estimates of treatment effectiveness when comparing outcomes across treatment groups from routine data (53,54). This section describes the target trial outcomes and analysis.

WP 3.1 Definition of time zero, primary and secondary outcomes and sample sizes

The target trial protocols require the definition of time zero, the analogue to randomisation in an RCT. For each of these target trials, we will define time zero as the treatment start date. At

this timepoint the eligibility criteria are met, and the patients included are 'assigned' to either the curative RT or surgical strategies. This time zero choice also minimises immortal time bias.

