Our overarching approach to combine insights from clinical and patient groups with advanced analytical methods used successfully in the NIHR-funded ESORT study evaluating emergency surgery ([name], [name], [name] & [name], 52-54). The ESORT study showed the importance of input from clinicians and patients in defining the main elements of the target trial's protocol, including eligibility criteria, and the treatment strategy protocols. For the assessment of the effectiveness of curative RT versus surgery, we will adjust for differences between the comparison groups in measured patient and organisational factors. However, we recognise that there is a risk of residual confounding from unmeasured differences between the comparison groups. We will address this risk of residual confounding in an instrumental variable analysis. An instrumental variable encourages receipt of the intervention, but does not have a direct effect on the outcome. The ESORT study showed how an instrumental variable analysis could reduce the risk of confounding when comparing outcomes from routine data (53,54). The proposed research draws on work by co-applicant [name] (41), who found that as curative RT requires more outpatient visits than surgery, patients who have to travel further may be less likely to receive curative RT. We will use the patient's travel time to the nearest RT centre, as an instrumental variable to minimise residual confounding after adjusting for all measured organisational and patient factors (see also WP 3).

4. Aims and objectives

The aims are to evaluate the impact of the COVID-19 period on inequalities in the use of curative interventions, and to assess the relative effectiveness and cost-effectiveness of RT versus surgery for patients with early-stage NSCLC, OSCC and MIBC.

For patients with these early-stage cancers, the objectives are:

- 1. To describe the influence of patient and organisational factors on the use of curative RT, curative surgery or non-curative strategies
- 2. To assess inequalities in the receipt of curative versus non-curative interventions
- 3. To assess the effectiveness of curative RT versus curative surgical strategies
- 4. To assess the cost-effectiveness of curative RT versus curative surgical strategies

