WP 1 will provide the foundation for the study. In WP 1.1 we will acquire and prepare the linked data and address issues concerning missing data and coding. We will develop 'working definitions' of the populations and comparators of interest. In WP 1.2 we will describe the influence of organisational and patient factors on the receipt of curative or non-curative interventions. In WP 1.3 we will present this information to three tumour-specific clinical panels each comprising of 8-10 clinicians involved in curative treatment decisions. The panels will refine the definitions of the populations, the treatment comparators, and offer insights on additional local factors that may influence the choice of curative or non-curative interventions for time periods prior to and during the COVID-19 pandemic. In WP 1.4 we will discuss the preliminary study protocol with the PPIE panel, who will provide advice on the study design and translation strategies. In WP 1.5 we will interview 10-15 patients with each early-stage cancer to find out about their experiences of the treatment pathways, and how we can provide information to improve the patient experience. We will draw on the insights from the clinical panels, the PPIE panel and the patient interviews for the final descriptive analyses (WP 1.6) and study protocols (WP 1.7).

WP 1.1 Initial data preparation and definition of study cohorts ([name], [name])

On notification of funding, we will access pilot data (Table 1) held in LSHTM's secure data environment according to pre-existing permissions for related research. The datasets will be checked for completeness and quality of linkage. We will create initial cohorts of patients aged 18 or older diagnosed with a first primary NSCLC or OSCC in England from 1.1.2015 to 31.12.2022 defined by ICD-10 (diagnosis) and ICD-0 (morphology) codes for the primary diagnosis using detailed tumour stage information. The MIBC cohort will include diagnoses from 1.1.2012 to 31.12.2022 as no new recommended RT therapy regimen emerged during this period for this type of cancer. These criteria will yield sample sizes of about 35,000 (NSCLC), 5,000 (OSCC) and 18,000 (MIBC). Eligible cohorts will have treatment categorised as curative RT, curative surgery or non-curative (WP2), and curative RT or curative surgery (WP3 and 4)

WP 1.2 Descriptive analysis of patterns of treatment and organisation of services ([name], advisor [name] on use of GIS software)

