We will use the linked datasets to define treatment pathways focussing on the period from diagnosis to curative and non-curative intervention for each tumour type. We will describe patients' sociodemographic, clinical and pre-diagnosis (e.g. time from referral) characteristics. At the organisation level (cancer alliance, NHS trust and hospital) we will recognise regional and temporal differences in how services have been centralised within the 'hub and spoke system'. We will describe the inter-relationships between treatment pathways, patient characteristics and the organisation of services. For example, we will report the numbers of NHS trusts that directly provide either curative RT or surgical services, provide neither, or offer both modalities. The way services are organised can influence care coordination, time to treatment, the patients' travel time, and access to curative RT, surgery or non-curative interventions. We will derive travel time data between each patient's area of residence, and the nearest centre providing each of the curative treatments using Geographic Information System (GIS) software (41). We will also consider the influence of the availability and volumes

of each service on the choice of curative intervention. For each cancer alliance we will describe relationships between organisations at different levels in providing curative RT, curative surgery and other oncology services, and if they have changed over time.

These descriptive findings will be presented to the clinical panels and will provide context for the synthesising the findings from WPs 2-4 (see dissemination and translation section).

Table 1: Data sources, and data categories that will be accessed from the linked NCRAS data ('the linked data')

Source	Key data categories
Cancer registration data	Demographics, diagnosis, tumour
	characteristics, travel time to centre
HES admitted patient-care, outpatient data	Comorbidities, frailty, surgical procedures,
	Resource use
RTDS	Radiotherapy, dose and fractionation,
	duration, and date
SACT	Chemotherapy and systemic therapy
	received, doses, duration and date
National audit data for NSCLC and OSCC	Performance status, organisational audit
	data.
Diagnostic and Imaging dataset	Resource use
Office of National Statistics (ONS) Mortality	All-cause death

HES: Hospital Episode Statistics, RTDS: National Radiotherapy Dataset, SACT: Systemic Anti-cancer Therapy Dataset

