WP 1.3 Clinical panels to refine the target trial protocols, and understanding of local organisational factors ([name], [name], [name], [name], [name])

The target trial protocols require definitions of the study cohorts and treatment strategies, and recognition of local organisational factors. We will convene clinical panels from multidisciplinary teams across the UK who are involved with the curative treatment decision. The panels will be presented with 'working definitions' of the study populations, treatment groups, and descriptions of the influence of patient and organisational factors on the receipt of curative and non-curative treatment strategies. The panels will be asked to refine the study eligibility criteria, the definition of the treatment groups, and to propose additional organisational factors that may influence the choice of curative treatment, beyond those measured in the linked data.

We will establish three tumour-specific clinical panels. Each panel will comprise 8-12 clinicians (oncologists and surgeons) involved in decision-making about curative treatments. Online meetings will allow involvement of panellists from different regions in England, who will meet for a three-hour facilitated discussion, led by the clinical co-applicants. Prior to the meetings, panellists will be provided with information packs including summaries of above descriptive analyses, and the provisional eligibility and treatment strategies for the target trials (see below). Panellists will be asked to complete surveys that improve these definitions, before and after the facilitated discussions.

Eligibility criteria

The provisional eligibility criteria and treatment strategies for the target trials (WP3), will be extracted from the cohorts with a first primary cancer diagnosis for each tumour type between 1.1.2012 and 31.12.2022 (MIBC) and 1.1.2015 and 31.12.2022 (NSCLC and OSCC) using the working criteria in Table 2. Inclusion of patients between these dates will ensure survival data are available for a minimum of three-years for all patients. Basic eligibility criteria for each cancer requires: (i) the appropriate tumour size (T), no cancer in lymph nodes (N0), cancer is

not metastatic (M0), and (ii) curative RT or surgery received within six months of diagnosis to ensure similarity of patient groups and curative intent.

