The instrumental variable approach will be set out in a Statistical Analysis Plan. In brief, we will draw from previous research that has used distance or travel time, as an instrumental variable for treatment choice (67). Recent work by co-applicant [name] found that travel time to the nearest RT centre from a patient's area of residence predicted whether they had curative RT or surgery (41). Our PPI colleagues have emphasised that increased travel time may discourage patients from having curative RT versus surgery as this requires more outpatient visits. We will calculate a continuous measure of travel time from the patient's area of residence to the nearest NHS trust that provides curative RT (see WP1). We will use this measure of travel time as an instrumental variable for the receipt of curative RT versus surgery. This instrumental variable will be combined with adjustment for measured covariates to minimise bias from unobserved confounding in comparing 3-year mortality following curative RT versus surgery, for eligible patients with each of these three early-stage cancers.

Box 1: Results from Pilot work supporting the Instrumental Variable approach

We undertook *preparatory work* using the 2014-17 national linked cancer data for early stage OSCC which has the smallest sample size across the 3 conditions, and hence presents a greater challenge for the instrumental variable approach. We found that the essential assumptions for travel time to be an instrumental variable were realistic. *First*, the travel time from the patients' area of residence to the nearest NHS trust providing curative RT was associated with receipt of curative RT versus surgery (F statistics >20 versus the recommended cut-off of >10). *Second*, travel time balanced prognostic measures such as the patients' cancer stage. We will repeat these assessments on the final linked data for all three conditions, which given the larger sample sizes would be anticipated to yield a stronger instrument. The assumption that travel time is independent of unmeasured confounders cannot be assessed empirically, but is likely to be justified, since after accounting for measured baseline variables (geographical place of residence, deprivation level, time period, 'centre' and other quality of care variables), it is unlikely that travel time direct predicts all-cause mortality. This assumption will also be discussed with the clinical panels (W1) (see also sensitivity analyses).

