WP 3.3 Estimating effectiveness of curative RT versus surgery for each tumour type

The three target trials will report differences between the comparison groups according to absolute risk differences for three-year mortality (primary endpoint) and other binary measures, and difference in means for continuous measures (secondary endpoints). We will use a local instrumental variable approach to estimate the relative effectiveness of RT versus surgery for each individual, as this approach can fully account for confounding and heterogeneity across patient subgroups (54). We will report relative effectiveness across all patients included in each target trial, and for each pre-specified subgroup of interest: tumour size and spread to nearby lymph nodes and/or to distant sites, age (years), performance status, smoking status, Charlson comorbidity index, and year of diagnosis. This analysis will

be conducted according to the intention-to-treat principle, recognising that patients may experience delays in the receipt of either curative intervention, may not complete their allocated treatment or may switch from one treatment option to the other. Following this principle, we will include all patients from the time they meet the inclusion criteria, and adjust for covariates anticipated to predict the assigned treatment and the outcome, according to their observed level at baseline (time zero).

The local instrumental variable approach comprises two stages. In the first stage, Probit regression models will be used to estimate the initial propensity score as a function of covariates and the IV. In the second stage, this predicted propensity score will be included alongside covariates in Generalised Linear Models with appropriate link functions for continuous or binary outcomes. Models at both stages will adjust for case-mix, organisational-and temporal factors described above including time period, proxies for care quality, defined by rates of 30-day and 1-year mortality for each NHS hospital trust for the early-stage cancers in question, for the year prior to the individual's diagnosis. The estimates will be reported with bootstrapped confidence intervals that allow for the clustering of individuals within NHS trusts and cancer alliances, and with multiple imputation to allow for missing covariate information.

WP 3.4 Sensitivity analyses

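### WP3 runs the travel-time IV analysis only in patients who received RT or surgery; if travel time also influences whether any curative treatment is given, the estimate may be biased, and the protocol plans no check

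*Protocol*

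**What the plan says.** WP 1.1 divides the cohorts by treatment category: "curative RT, curative surgery or non-curative (WP2), and curative RT or curative surgery (WP3 and 4"). Patients without curative treatment are therefore analysed in WP2 only. WP 1.3 makes treatment receipt a basic eligibility criterion for the target trials: "curative RT or surgery received within six months of diagnosis to ensure similarity of patient groups and curative intent". In WP 3.1, "we will define time zero as the treatment start date". WP 3.3 invokes intention to treat and states that "we will include all patients from the time they meet the inclusion criteria"; since those criteria include having been treated, this does not bring untreated patients back.

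The instrument is defined in WP 3.2: "We will use this measure of travel time as an instrumental variable for the receipt of curative RT versus surgery". Its rationale is that RT needs more outpatient visits, so "patients who have to travel further may be less likely to receive curative RT" (section 3.4). The alternative the protocol has in mind is surgery.

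WP 2.1 extracts travel time to the nearest centre for each curative treatment, and WP 2.2 includes distance to centre in its models of RT and surgery versus no curative treatment.

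Box 1 covers instrument strength, balance on measured prognostic factors such as stage, and independence from unmeasured confounders. WP 3.4 lists four sensitivity analyses: a three- or nine-month treatment window, a trust-level instrument, conventional risk adjustment with an assessment of unobserved confounding, and exclusion of the first COVID-19 wave. All four stay within treated patients.

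**The concern.** A patient unfit for surgery who is deterred from RT by distance cannot switch to surgery and would leave the WP3 sample. A similar patient living near an RT centre has RT and stays in. If this happens often enough, included patients who live near are less fit than included patients who live far away. Travel time then carries information about prognosis in the analysed sample, even if it carried none among all diagnosed patients.

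The protocol makes the prognosis side of this plausible: section 3.4 calls fitness for surgery a key factor before COVID-19, and the risk table in section 11 accepts that RT patients may be sicker. The IV analysis is the main defence against unmeasured confounding in WP3, and WP4 reuses the same instrument, so any bias would carry into the cost-effectiveness results.

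**Working it through.** **Planning figures.** This point disputes no stated number, but Table 3 gives the scale. With N = (1.960 + 0.842)² × SD² / [p(1−p) × c² × δ²], where c is compliance, p the RT share and δ the risk difference (two-sided 5% assumed, since alpha is not stated), the first cell is 7.849 × 0.09 / (0.25 × 0.25 × 0.0025) = 4,521, as printed. All 18 cells reproduce to within one patient.

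**Formula.** With no true effect, and near and far groups compared:

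bias = (mortality near − mortality far, among included patients) / (RT share near − RT share far).

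The numerator is zero if receipt of curative treatment does not depend on travel time, or does not depend on unmeasured prognosis. If nearness retains less fit patients, it is positive and RT looks worse.

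**Illustration A (deliberately severe; all inputs assumed).** Half the cohort is fit and always treated. Half is frail: 20% are treated if far and 20% + x if near, all with RT. Three-year mortality is 30% in fit and 52% in frail patients, a gap of 22 points. Far, 60% are treated and the frail share among them is 0.10/0.60 = 0.167.

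| x | Gain in any curative treatment | Frail share, near | Change × 0.22 | Bias at c = 0.7 | Bias at c = 0.5 |
|---|---|---|---|---|---|
| 0.02 | 1 point | 0.11/0.61 = 0.180 | 0.0030 | 0.4 | 0.6 |
| 0.04 | 2 points | 0.12/0.62 = 0.194 | 0.0059 | 0.8 | 1.2 |
| 0.10 | 5 points | 0.15/0.65 = 0.231 | 0.0141 | 2.0 | 2.8 |

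With first-stage differences of 0.13, 0.14 and 0.16, the same three rows give 2.3, 4.2 and 8.8 points.

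**Illustration B (graded frailty; all inputs assumed).** 60% are treated on average. Unmeasured frailty is normally distributed, with a mortality odds ratio of 1.5 to 2 per SD, an odds ratio for curative treatment of 0.33 to 0.5 per SD, and mortality of 25% at average frailty.

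| Fall in any curative treatment, near to far | Bias at c = 0.5–0.7 | Bias at c = 0.1 |
|---|---|---|
| 0 | 0 | 0 |
| 2 points | 0.1–0.4 | 0.9–2.0 |
| 5 points | 0.3–1.0 | 2.2–5.0 |
| 10 points | 0.6–2.0 | 4.5–10.0 |

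A exceeds B for the same change because A makes every marginal patient frail.

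**Which first stage?** Table 3 assumes 0.5 to 0.7. The reported pilot evidence is F > 20. For two equal halves and an RT share near one half, F = n × d², where d is the near–far difference in RT share. F = 20 then corresponds to d = √(20/3,000) = 0.08 or √(20/1,500) = 0.12 (both n assumed). F > 20 is only a lower bound on strength, but it does not demonstrate 0.5. A larger sample raises F without raising d, and d is what scales the bias.

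**Consequence.** SE = SD / [c × √(N p(1−p))]. With SD 0.4, c = 0.5 and p = 0.5, SE is 2.9 points at N = 3,000 (the OSCC target trial) and 1.1 points at N = 20,000 (NSCLC). A 1-point bias raises the 5% two-sided error to 6.4% and 14%; a 2-point bias raises it to 10.5% and 42%.

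**The case against.** A reader might infer that the protocol itself says travel time affects receipt of any curative treatment, and hence that the estimate is biased. The text does not support that. WP 1.2 says that the organisation of services can influence "the patients' travel time, and access to curative RT, surgery or non-curative interventions", among other things: travel time and access are parallel consequences of organisation, not cause and effect. Section 3.4 and WP 3.2 concern RT against surgery. Listing distance as a WP2 covariate asserts no effect. This objection stands, and the point is therefore conditional.

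Adjustment also narrows the problem. The linked data hold comorbidity and frailty scores, and both stages of the local IV model adjust for case-mix, organisational and temporal factors, so only residual prognosis matters. The illustrations ignore this and overstate the bias to that extent. Adjustment may be thinner for MIBC, since Table 1 sources performance status from audits for NSCLC and OSCC only.

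Nor is the IV the sole protection. There are prognosis-based exclusions, a second instrument, and conventional adjustment with an assessment of unobserved confounding. None of these addresses selection into the treated sample.

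The drop from 5,000 to 3,000 in OSCC (40%) might be read as the share without curative treatment. The protocol does not say so, and other exclusions apply, so the 60% treated is an assumption.

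The eligibility criteria are provisional and IV detail is left to an SAP that is not shown. That is fair for methods detail. But WP 1.1 already confines non-curative patients to WP2, and WP 3.4 sets out its list of sensitivity analyses without this one.

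Finally, WP 3.1 says: "This time zero choice also minimises immortal time bias". One might infer either that this settles the matter or that the claim should be struck out. Neither follows. Starting follow-up at treatment credits neither arm with earlier survival, but it does not change who enters. Whether neoadjuvant chemotherapy counts as treatment start is a separate clarification.

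**Conclusion.** The concern holds as a conditional risk. The sample rule can make travel time associated with unmeasured fitness, and the IV estimate may then be biased, probably against RT. Two conditions must both hold after covariate adjustment: travel time influences receipt of any curative treatment, and receipt depends on unmeasured prognosis. The documents establish neither. If either fails, this bias is zero.

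At the planned compliance of 0.5 to 0.7 the illustrations give roughly 0 to 3 points. With a first stage near 0.1 to 0.16 they reach the 5- to 10-point range that the study aims to detect. These sizes rest on assumed frailty effects and are not estimates for this study. The first condition can be tested with data the study will already hold, and the protocol does not plan to use them as a check on the instrument. This is an inexpensive improvement, not evidence that the design fails.

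**What to change.** 1. Before WP3, in the full early-stage WP2 cohort for each tumour type, regress receipt of any curative treatment within six months on travel time to the nearest RT provider, with the WP3 covariates. Report it with the Box 1 assessments as an IV validity check. Give the estimate and interval beside the first-stage difference over the same travel-time contrast, since their ratio drives the bias.
2. Add to WP 3.4 a sensitivity analysis that uses inverse-probability-of-selection weights in the local IV analysis, bounds for unmeasured selection, or both. State that the weights correct only for measured selection. Carry the same analysis into the WP4 scenarios.
3. Optionally, report three-year mortality by travel time in all diagnosed patients who meet the clinical criteria, whatever their treatment. Label it supportive: it mixes RT, surgery and no curative treatment, so it does not isolate RT versus surgery.

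The cost is extra analysis on data already in the linked extract and slightly wider intervals in the weighted analysis. The primary analysis and sample need not change.
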